9.3.1. Provision of follow-up information

For all serious adverse events identified and reported during the study, participants should be followed up until resolution or stabilisation of the event. Follow-up information should be provided on a SAE Follow-up form.

9.4. Reference Safety Information

The Reference Safety Information (RSI) will be the SmPC’s as described below:

For the COC treatment participants prescribed Microgynon 30 or an equivalent the RSI will be Microgynon 30 tablets (levonorgestrel, ethinylestradiol) Bayer plc.

For the HRT treatment participants prescribed an oral formulation the RSI will be Femoston 2/10mg film-coated tablets (oestradiol, dydrogesterone) Mylan Products Ltd.

For the HRT treatment participants prescribed a transdermal patch the RSI will be EVOREL SEQUI (estradiol hemihydrate, norethisterone acetate) Theramex UK Limited.

For the HRT treatment participants prescribed a transdermal gel the RSI will be Oestrogel Pump-Pack 750 micrograms/actuation gel (estradiol) Besins Healthcare (UK) Limited.

Any updates to the RSI will be reviewed annually in line with the Development Safety Update Report (DSUR).

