1.2.3. Choice of treatment

Two preparations are widely prescribed in the UK as oestrogen replacement for women with POI, HRT and COC. HRT is based on physiological oestrogen (17β oestradiol) and usually contains synthetic progestogen although alternatives (natural progesterone, intrauterine progestogen) are available; treatment may be oral or transdermal. The COC contains ethinylloestradiol, a synthetic oestrogen with significant metabolic impact, and synthetic progestogen.

The trial is a two-group design, with participants randomised to receive either HRT or the COC. The type and dose of oestrogen is specified. The type and dose of progestogen is specified, as far as practicable given the preparations available, to standardise the treatments used.

In view of the variety of available hormonal preparations, some with added contraceptive properties, it is neither practical nor ethical to blind the treatments to the women or treating clinicians.

HRT:

The trial mandates that the HRT preparation contains 17β-oestradiol. This is available via oral and transdermal routes, the latter being the preferred choice of half of the clinicians surveyed when designing the trial. However, transdermal HRT may not be as acceptable to women as oral tablets, and patches may cause skin irritation, acknowledged by our patient survey, so the trial will not specify which formulation is used. It is acknowledged that the pharmacodynamics differ. Therefore, it is required that the **oestradiol daily starting dose is 2mg orally or 50µg patch or 1.5mg gel transdermally** (these are considered clinically equivalent). Dose will not be titrated by serum oestradiol measurement as this is not done in clinical practice and of limited value in oral therapy.

Women with POI and an intact uterus require progestogen to protect against endometrial hyperplasia; progestogen may be given cyclically or continuously. This will not be mandated, as the trial design survey indicated that the formulation used was predicated on the need for contraception or other patient preferences, with 15 out of 42 of HRT prescribers surveyed offering the levonorgestrel-releasing intrauterine system (LNG-IUS) and the same number oral micronised progesterone. Women who are not using the LNG-IUS will be informed of the small chance of spontaneous pregnancy in POI and advised to use non-hormonal contraception if required.

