7.1.1. HRT

Women randomised to receive treatment with HRT should be prescribed oestradiol in a **daily dose** of 2mg orally, or a 50µg patch, or 1.5mg of gel, given continuously.

Women with a uterus will also be prescribed progestogen, taken cyclically or continuously. The formulation is not mandated. The preferred oral formulation is oestradiol 2mg with dydrogesterone 10mg (Femoston 2/10), and the preferred transdermal formulation is oestradiol 50µg with norethisterone 170µg patch (Evorel Sequi). Alternative formulations can be prescribed if required but must contain oestradiol as mandated above, for example oestradiol gel with micronised progesterone or LNG-IUS.

Women who are not using the LNG-IUS will be advised to use non-hormonal contraception if required.

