7.1.2. COC

Women allocated the COC should be prescribed 30µg ethinyloestradiol with 150µg levonorgestrel (Microgynon 30 or equivalent) as an extended regimen; the suggested regimen is 63 days with 7 days hormone-free interval. Alternative formulations can be prescribed if required but must contain 30µg ethinyloestradiol in a monophasic formulation.

Use of a contraceptive patch or ring is not permitted.

Table 2: Summary of treatment options for initiating randomised treatment

Treatment Group	Permitted route(s) of administration	Formulation/Specified dose	Administration/additional information
COC	Oral	Monophasic tablets containing 30µg ethinyloestradiol	Tricycling for 63 days of tablets followed by a 4-7 day hormone-free interval, or flexible extended use, taking continuously with short breaks of 3-4 days if breakthrough bleeding occurs. The preferred regimen is tricycling for 63 days of tablets followed by a 7-day hormone-free interval.
HRT	Oral	Containing 17β-oestradiol. Starting dose: 2mg daily.	Women with POI and an intact uterus require progestogen to protect against endometrial hyperplasia; progestogen may be given cyclically or continuously.
	Transdermal	Containing 17β-oestradiol. Starting dose: Patch: 50µg oestradiol daily Gel: 1.5mg oestradiol daily	

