Investigators will report all AEs that they become aware of that meet the definition of an SAE, including those adverse events collected via patient questionnaire as mentioned in section 9.2.

AEs defined as serious, and which require reporting as an SAE should be reported on an SAE form. When completing the form, the Investigator will be asked to define the causality and severity of the AE. The SAE form must be sent to the NCTU as soon as possible and no later than 24 hours after first becoming aware of the event (or obtaining the follow-up information from the participant).

On receipt NCTU will allocate each SAE a unique reference number which will be forwarded to the site as proof of receipt within 1 working day. If confirmation is not received within 1 working day sites should contact the NCTU. The SAE reference number will be quoted on all correspondence and follow-up reports regarding the SAE and filed with the actual SAE in the Site File and TMF.

Sites

For SAE Forms completed by someone other than the Investigator, the Investigator will be required to countersign the original SAE Form to confirm agreement with the causality and severity assessments. The form should then be returned to NCTU and a copy kept in the Site File. Investigators should also report SAEs to their own Trust in accordance with local practice.

On becoming aware that a participant has experienced an SAE, the Investigator (or delegate) must complete, date and sign a SAE form. The form should be e-mailed to NCTU using the following e-mail address:

FOR SAE REPORTING ONLY: [contact]

Trial name:	Premature Ovarian Insufficiency Study of Effectiveness of hormonal therapy	Protocol version:	4.0	date:	01 Oct 2024	Page:	37
-------------	--	-------------------	-----	-------	-------------	-------	----

NCTU

On receipt of an SAE Form seriousness and causality will be reviewed independently by the medical monitor responsible for determining causality assessments. An SAE judged by the Investigator or medical monitor (in this case the CI), to have a reasonable causal relationship with the trial medication will be regarded as a Serious Adverse Reaction (SAR). The medical monitor will also assess all SARs for expectedness. If the event meets the definition of a SAR that is unexpected (i.e. is not defined in the Reference Safety Information (RSI) –see Section 9.4) it will be classified as a SUSAR.

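### Section 9.4 sets the reference safety document by oestrogen route, so permitted progestogens have no matching document and expectedness can be misjudged in either arm

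*Protocol*

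**What the plan says.** Section 9.4 names four product documents as RSI.

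- COC: "For the COC treatment participants prescribed Microgynon 30 or an equivalent the RSI will be Microgynon 30 tablets (levonorgestrel, ethinylestradiol", so both hormones are covered.
- Oral HRT: "For the HRT treatment participants prescribed an oral formulation the RSI will be Femoston 2/10mg film-coated tablets (oestradiol, dydrogesterone", a combined product.
- Patch: "For the HRT treatment participants prescribed a transdermal patch the RSI will be EVOREL SEQUI (estradiol hemihydrate, norethisterone acetate", also combined.
- Gel: "For the HRT treatment participants prescribed a transdermal gel the RSI will be Oestrogel Pump-Pack 750 micrograms/actuation gel (estradiol", with oestradiol as the only active ingredient.

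The permitted regimens are wider than this list. The trial summary and section 7.1.1 make a progestogen part of HRT for women with a uterus and do not mandate its formulation. Femoston 2/10 and Evorel Sequi are the preferred products. Alternatives are allowed, "for example oestradiol gel with micronised progesterone or LNG-IUS". On the COC side, section 7.1.2 says: "Alternative formulations can be prescribed if required but must contain 30µg ethinyloestradiol in a monophasic formulation".

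Section 9.3 then gives the rule that uses the RSI: "If the event meets the definition of a SAR that is unexpected (i.e. is not defined in the Reference Safety Information", in which case the event is classified as a SUSAR. Section 9.1 defines unexpectedness against the product information that applies, which for a licensed product is its SmPC. Section 9.7.1 sets the expedited reporting times: 7 days for fatal or life-threatening SUSARs and 15 days for the others.

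**The concern.** The RSI is chosen by how the oestrogen is given, but the treatment is often two products, and the progestogen can be chosen separately from the oestrogen. For some permitted regimens the document therefore omits a component the woman takes. For others it lists one she does not take.

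The two errors run in opposite directions. If a component is missing, a known reaction to it can be called unexpected and sent for expedited reporting without need. If the document lists a hormone the woman is not taking, a reaction that is unexpected for her regimen can be passed as expected and not expedited. The second is the less safe error. At stake are the 7- and 15-day reports in section 9.7.1 and the SUSAR notices to Principal Investigators in section 9.8.

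**Working it through.** The protocol gives no figure to reproduce on this point. The check sets each regimen permitted by sections 7.1.1 and 7.1.2 beside the document that section 9.4 assigns to it.

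| Permitted regimen | Document under 9.4 | Match |
|---|---|---|
| Femoston 2/10 | Femoston 2/10 | Both hormones covered |
| Evorel Sequi patch | Evorel Sequi | Both hormones covered |
| Oral oestradiol with micronised progesterone or LNG-IUS | Femoston 2/10 | Document carries a different progestogen (dydrogesterone) |
| Patch with micronised progesterone or LNG-IUS | Evorel Sequi | Document carries a different progestogen (norethisterone acetate) |
| Gel with micronised progesterone or LNG-IUS | Oestrogel | No progestogen in the document |
| Oral oestradiol alone, after hysterectomy | Femoston 2/10 | Document adds a progestogen not taken |
| Microgynon 30 | Microgynon 30 | Both hormones covered |
| Other monophasic 30µg COC with a different progestogen | Unclear | Section 9.4 covers only Microgynon 30 or an equivalent, and does not define equivalent |

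Three steps follow.

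1. The gel row needs no assumption about use. Any gel user with a uterus must also have a progestogen, and her RSI contains none.
2. The oestradiol-only row is not hypothetical. Section 4.1 accepts surgical menopause, and section 13.3.4 plans a subgroup by hysterectomy.
3. Section 9.3 sends any SAR not defined in the RSI to the SUSAR category. Read literally, sections 9.3 and 9.4 make the assessor use the route document even where section 9.1 would point to the document of the product in use. The sections do not fit together for these regimens.

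The only related count in the protocol is the design survey in section 1.2.3, "with 15 out of 42 of HRT prescribers surveyed offering the levonorgestrel-releasing intrauterine system (LNG-IUS) and the same number oral micronised progesterone". The shares are:

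- each product: 15/42 = 35.7% of surveyed prescribers;
- either product, if the two groups overlap fully: 15/42 = 35.7%;
- either product, if they do not overlap: (15 + 15)/42 = 30/42 = 71.4%.

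These are shares of prescribers who offer a product, not of participants who use it. They show that the uncovered products are in ordinary use among those surveyed. They do not give the number of women, or of reactions, affected.

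**The case against.** The best defence is that one representative document per route is a deliberate simplification in a low-risk Type A trial of licensed products (section 7.2.2). The medical monitor assesses every SAR for expectedness, section 9.1 already points to the product information that applies, and RSI updates are reviewed yearly. Where a progestogen is missing from the RSI, the error tends towards over-reporting, which is the cautious direction.

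Part of this stands. The effect is confined to expectedness and expedited reporting. The annual report includes all SAEs and SARs (section 9.7.2), the DMC reviews all SAEs (section 9.9), and adverse events are summarised descriptively by allocated group and by treatment received (section 13.3). No comparison or stopping rule uses SUSAR counts. The defence does not remove the defect, however. Section 9.3 ties the decision to the RSI in section 9.4, yearly review of the listed documents does not add missing ones, and for oral oestradiol alone the error can run towards under-reporting.

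A reader might infer more than the protocol supports.

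- That only the preferred HRT products are covered. Oestrogel is listed and is not a preferred product, and both preferred products are covered for both hormones.
- That a given progestogen reaction is a SUSAR under HRT and expected under COC, so SUSAR counts are biased against HRT. The contents of the product documents are not in the protocol, so no event can be shown to be classified differently. An assigned document may list the same event. The COC arm has its own gap. Levonorgestrel is the one shared substance: it appears in the COC document and in none of the HRT documents although the LNG-IUS is permitted. That shows a different reference standard, not a demonstrated difference in classification.
- That 36% to 71% of HRT women are affected. Those figures describe what prescribers offer, and section 7.1.1 steers sites to the preferred products.

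**Conclusion.** The point holds as a mismatch between sections 7.1.1, 7.1.2 and 9.4. The RSI has no document for micronised progesterone or the LNG-IUS, gives gel users with a uterus an oestradiol-only document, gives users of oral oestradiol alone a combined one, and is unclear for COCs with a progestogen other than levonorgestrel. Under section 9.3, expectedness of progestogen- or device-related SARs can therefore be misclassified in either arm and in either direction.

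The size cannot be estimated. The protocol gives no counts of participants by progestogen, no rate of serious reactions and no content of the product documents. Serious related reactions are expected to be few, so the number misclassified is expected to be small. The conclusion assumes that sections 9.3 and 9.4 are applied as written. The BMD analysis is untouched. The point merits a text correction because it concerns a stated reporting rule with regulatory time limits.

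**What to change.** Reconcile sections 7.1.1, 7.1.2 and 9.4 by defining the RSI by each component of the permitted regimens.

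- Keep the four listed documents for the products they describe.
- Add product documents for micronised progesterone, the LNG-IUS and oral oestradiol alone.
- Add the relevant document for each permitted COC with another progestogen, and say what counts as equivalent to Microgynon 30.
- State in section 9.3 that expectedness is judged against the components the woman was taking, in line with section 9.1.

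The cost is an amendment to the RSI section and a few more documents in the annual review. It needs no additional participants. The assessor must look up the regimen in use: section 7.6 already has dose and formulation changes recorded in the eCRF, and Table 3 collects medication use at baseline and each follow-up.

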9.5. Reporting period

Details of AEs (except those listed in section 9.2) will be documented and reported from the date of commencement of protocol defined treatment until 2 years after randomisation of the last participant.

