2.2. Outcome Measures

2.2.1. Primary outcome:

Absolute BMD (g/cm²) at 2 years from the date of randomisation, assessed by a standard DEXA scan of the lumbar spine.

2.2.2. Secondary outcomes:

The secondary outcomes will be measured at different stages throughout the trial.

- Absolute BMD (g/cm²) in lumbar spine at 1 and 2 years.
- Absolute BMD (g/cm²) in hip at 1 and 2 years.
- T-score category (≤ -2.5 , > -2.5 to ≤ -1 , > -1) for BMD at lumbar spine at 1 and 2 years.
- T-score category for BMD at hip at 1 and 2 years.

Trial name:	Premature Ovarian Insufficiency Study of Effectiveness of hormonal therapy	Protocol version:	4.0	date:	01 Oct 2024	Page:	20
-------------	--	-------------------	-----	-------	-------------	-------	----

- Individual domains (vasomotor, psychosocial, physical and sexual) and summary score of Menopause Specific Quality of Life (MENQOL-I)-Intervention questionnaire at 3, 6 and 12 months then annually.
- Sexual function (pleasure, discomfort and frequency) measured by the Sexual Activity Questionnaire (SAQ)² at 3, 6, 12 months then annually.
- Work Productivity (absenteeism, presenteeism, work productivity loss and activity impairment), using the Work Productivity and Activity Impairment (WPAI) Scale (Specific health Problem)³ at 3, 6, 12 months then annually.
- Weight (kg) at 3, 6, and 12 months then annually.
- Systolic blood pressure (mm Hg) at 3, 6 and 12 months then annually.
- Diastolic blood pressure (mm Hg) at 3, 6 and 12 months then annually.
- Pregnancy and pregnancy outcome.
- Satisfaction with treatment, on a 5-point Likert scale at 3, 6 and 12 months then annually.
- Change or cessation of treatment at 3, 6 and 12 months then annually.
- Adverse events at 3, 6 and 12 months and then annually. Specific minor-side effects collected will include breast pain, nausea, headaches, skin or hair changes and unscheduled bleeding (see Section 9.2) as well as more serious events such as venous thromboembolism. All serious adverse events will be collected and causal relationship with treatment considered.
- Diagnosis of cancer, cardiovascular disease, cognitive impairment, bone fractures and mortality will be collected from routine data sources up to 5 years.

Sub-study

- Bone metabolism markers, liver function tests, bone profile, and 1,25 Vitamin D. Blood and urine samples will be collected in a subset of participants from selected sites, at baseline, 3 and 12 months (not reported until the end of the study).

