8.2. Schedule of Assessments

8.2.1. Enrolment and baseline

a) Identify potentially eligible patient

All potentially eligible patients should be approached and provided with information about the trial. This information will be entered onto the patient screening/enrolment log at each recruiting site. Patients that decline participation are not obliged to give a reason, however this will be recorded where this is known. Sites will be required to provide a summary of screening data on an ongoing basis during the recruitment period which will be reviewed regularly by the Trial Management Group (TMG) and oversight committees.

b) Informed Consent

Informed consent will be obtained as described in section 5. If a patient requires a washout period then eligibility will need to be re-confirmed prior to collecting baseline data.

c) Washout

Eligible women who are already on COC/HRT/testosterone treatment are required to stop treatment for a washout period of a minimum of 4 weeks. This is to ensure a return to pre-treatment hormone levels before performing baseline assessments.

d) Confirm Eligibility

Eligibility will be confirmed by the principal investigator or delegated trial doctor using the eligibility checklist form once informed consent and baseline data have been obtained.

e) Baseline data collection

After informed consent (and washout if applicable), baseline visit data will be collected by a member of the site research team and will include:

1. Patient demographics
2. Lifestyle factors e.g. smoking, alcohol, exercise habits
3. Use of medication e.g. prescribed, complementary and supplements
4. Pregnancy and breastfeeding
5. BMD (DEXA bone density measurement of lumbar spine and hip)
6. Quality of life (MENQOL-I questionnaire)
7. Sexual function (SAQ)
8. Work productivity (WPAI questionnaire)
9. Blood pressure (BP) and weight (refer to details below for BP measurement)
10. Height (measured at visit)
11. Blood and/or urine samples for bone and CVD biomarkers (selected sites only)

Trial name:	Premature Ovarian Insufficiency Study of Effectiveness of hormonal therapy	Protocol version:	4.0	date:	01 Oct 2024	Page:	31
-------------	--	-------------------	-----	-------	-------------	-------	----

12. Karyotype analysis (selected sites only and if clinically appropriate and not done prior to entering trial.

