8.3. Trial Procedures

The availability of DEXA scan appointments at some sites may result in time delays, specifically if the participant requires a baseline scan. If the participant has not had a DEXA scan in the 6 months prior to the date of randomisation then baseline assessments and randomisation should be delayed until this can be performed. Where possible all DEXA scans throughout the duration of the study for a participant should be completed on the same machine.

Throughout the study, reminders and updates will also be shared with participants via a range of media such as newsletters, websites, text message reminders and social media platforms.

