9.2. Adverse Events and reporting requirements/procedures

The collection and reporting of Adverse Events (AEs) will be in accordance with the Medicines for Human Use Clinical Trials Regulations 2004 (and subsequent amendments).

All IMPs (HRT and COC) being used in this trial are licensed and have well characterised safety profiles.

All preparations of HRT used in this trial are licensed for use for oestrogen deficiency symptoms in post- and peri-menopausal women.

Whilst the COC is licensed as an oral contraceptive it is not licensed specifically for treating oestrogen deficiency and POI. It is however widely, prescribed for the treatment of POI; this off-label use is standard practice and all treatments used in the trial have well-established safety profiles.

In order to provide secondary outcome data about the adverse events associated with the use of the COC or HRT, only specified adverse events will be collected.

The following expected AEs will be participant-reported and collected using a questionnaire at 3, 6, 12 months and yearly up to 5 years, depending on the point at which the participant joins the trial. If a

Trial name:
	
Premature Ovarian Insufficiency Study of Effectiveness of hormonal therapy
	
Protocol version:
	
4.0
	
date:
	
01 Oct 2024
	
Page:
	
36

--------------------	---	--------------------------	------------	--------------	--------------------	--------------	-----------

clinic visit is not possible or a participant fails to attend, questionnaires will be provided to participants electronically so they can be completed remotely.

Participants will be asked at each follow-up visit if they have experienced any of the following:

- Unscheduled bleeding
- Breast pain
- Nausea
- Headaches
- Skin or hair changes (acne/facial spots, greasy or oily skin, hair loss/hair thinning, hirsutism (=excessive hair growth on face or body))
- Dysmenorrhoea (period pains)
- Menorrhagia (heavy periods)
- Premenstrual syndrome (PMS)
- VTE or pulmonary embolism (PE)
- Broken bone(s)

Where any of the above events result in an admission to hospital or prolongation of a hospital stay this will also require reporting on a SAE form by the Principal Investigator or delegate (see section 9.3).

Adverse events will be coded using the Medical Dictionary for Regulatory Activities (MedDRA) as per NCTU standard practice.

9.3.Serious Adverse Events and reporting requirements

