- Adjustment for any other baseline variable (if applicable) with marked imbalance between the two treatment groups

Supplementary analyses for the primary outcome will investigate potential effects of compliance with allocated treatment using complier average causal effect (CACE) analysis (or per-protocol analysis should there be high crossover rates making CACE identification impossible) and estimate an overall time-averaged between-group effect over the 2 years to compare the overall rate of change in BMD between groups.

Main analyses of secondary outcomes will be based on intention-to-treat, analysing participants in the groups to which they were randomised, regardless of adherence with allocation. Sensitivity analyses (as described for the primary outcome) may also be performed for key secondary outcomes such as blood pressure, MENQOL-I, and BMD at 1 year and 2 years. Ordered logistic regression models will be used to compare the total lumbar spine and hip T-score categories (≤ -2.5 , > -2.5 to ≤ -1 , > -1) between groups, adjusted for the minimisation variables; however, should there be only a small number of participants in one of the categories then categories will be collapsed into two for analysis and logistic regression used. Between-group comparison of secondary outcomes will be based on an appropriate regression for the outcome adjusted for the minimisation variables and baseline outcome measure for continuous variables if available. For repeated measures, appropriate mixed-effect models for the outcome (linear for continuous outcomes and logistic for binary), adjusted for the minimisation variables, will be used to estimate the difference between groups at each time point. Supplementary analysis of key secondary outcomes may also be conducted according to actual treatment used if the percentage of women who stop using their allocated treatment or switch to the other treatment is high.

Adverse events will be presented descriptively only and will be summarised according to both the allocated group and the treatment received.

Trial name:	Premature Ovarian Insufficiency Study of Effectiveness of hormonal therapy	Protocol version:	4.0	date:	01 Oct 2024	Page:	44
-------------	--	-------------------	-----	-------	-------------	-------	----

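### Section 9.5 opens SAE reporting only when allocated treatment starts, so it leaves out the trial-required washout and, for events outside the 9.2 list, randomised women before or without a first dose

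*Protocol*

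**What the plan says.** **When reporting starts.** Section 9.5 sets the window: "from the date of commencement of protocol defined treatment until 2 years after randomisation of the last participant". It carves out one class of event at the start of the same sentence: "Details of AEs (except those listed in section 9.2) will be documented and reported from the date of commencement of protocol defined treatment".

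**What is collected.** Section 9.2 states that "only specified adverse events will be collected". The list includes venous thromboembolism, pulmonary embolism and broken bones. It is put to participants at each follow-up visit, and any listed event that leads to admission or a longer stay also goes on an SAE form. Section 9.3 requires investigators to report every SAE they learn of, including those found through the 9.2 questionnaire, and gives no start date. Section 2.2.2 says: "All serious adverse events will be collected and causal relationship with treatment considered".

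**Washout.** Section 8.2.1 c): "Eligible women who are already on COC/HRT/testosterone treatment are required to stop treatment for a washout period of a minimum of 4 weeks". Section 5 requires consent before washout begins. No maximum length is stated.

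**Analysis.** Under section 13.3 adverse events are descriptive only and "will be summarised according to both the allocated group and the treatment received".

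**The concern.** A reporting window that opens at first dose is common, and usually harmless, because little is done to participants before then. Here the trial does act before then: it asks consented women to stop hormone treatment. Section 7.1 gives the reason as a realistic baseline assessment of symptoms and quality of life, while section 1.1 says that professional bodies recommend long-term treatment. If a woman has a serious event in that interval, no part of the protocol tells the site to record it as a safety event. The Data Monitoring Committee, which under 9.9 reviews all SAEs, would then not see it.

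After randomisation the question is one of coverage. If sites follow 9.5, an unlisted SAE counts only in women who have started their allocation. Starting is a post-randomisation event and, in an open trial, could differ between arms. Section 7.2.1, for example, notes that in England HRT is typically charged for while the COC is free. Listed events and unlisted SAEs would also be counted over different periods within one safety summary.

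**Working it through.** The protocol gives no figure to reproduce, so the check is a reading of the sections against each other.

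**Step 1: what 9.5 actually governs.** It covers adverse events except those in the 9.2 list. Section 9.2 says that non-serious events off the list are not collected. What remains for 9.5 is SAEs not on the 9.2 list, which the section does not say.

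**Step 2: apply the rules to each group.**

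| Group and event | 9.5 window | Other provision | Covered? |
|---|---|---|---|
| Consented, in washout, any SAE | Not open | The 9.1 definition needs a participant who has been given a medicinal product; Table 3 has no adverse-effect entry before 3 months | No provision found |
| Found ineligible after washout | Never opens | Section 5.1 keeps the consent documents and the reason for ineligibility | No provision found |
| Randomised, before first dose, unlisted SAE | Not open | 9.3 duty has no start date; 2.2.2 promises all SAEs | Sections conflict |
| Randomised, never starts, unlisted SAE | Never opens | As above; 8.5 continues follow-up regardless of treatment use | Sections conflict |
| Randomised, never starts, 9.2-listed event | Exempt from 9.5 | Asked at 3, 6 and 12 months, then yearly; SAE form if admitted (9.2), and 9.3 | Yes |
| Randomised, never starts, death, cancer, cardiovascular disease, cognitive impairment or fracture | Not needed | Routine data up to 5 years (2.2.2), collected at 5 years (8.2.2) | Yes as an outcome, not as a timely safety report |

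**Step 3: effect on the planned summary.** Section 13.3 summarises events by allocated group. Under 9.5 the women contributing unlisted SAEs are those allocated to the arm who also started treatment, whereas those contributing listed events are all who were allocated and followed. The two parts of the table therefore rest on different populations and start dates.

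**Step 4: can the gap be sized?** The expected number of SAEs outside the window is

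(women in washout × washout length × SAE rate) + (starters × delay from randomisation to first dose × unlisted SAE rate) + (never-starters × follow-up × unlisted SAE rate).

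The protocol supplies only lower limits on two durations: 4 weeks for washout and 2 years for follow-up. It gives none of the numbers of women, the delay to first dose or the event rates. No estimate is possible without inventing inputs.

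**Step 5: a related inconsistency.** Sections 6.1 and 8.3 accept a DEXA scan from the 6 months before randomisation, while 8.2.1 e) lists bone density among the data collected after consent and washout. Where no recent scan exists, 8.3 says that "baseline assessments and randomisation should be delayed until this can be performed". The text does not settle whether the scan comes before or after washout, and so whether a wait for a scan can lengthen the interval without safety reporting.

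**The case against.** The strongest reply is that 9.5 is consistent with 9.1, which ties an adverse event to a participant who has been given a medicinal product, and that starting SAE collection at consent is largely a design preference. Washout precedes randomisation and so cannot bias the comparison between arms. Adverse events are descriptive, so no formal safety test is at risk. The undated duty in 9.3 may lead sites to report early events anyway. All of this stands, and it limits the weight of the point. It does not remove the conflict: 9.3 and 2.2.2 tell sites one thing and 9.5 another, and no section covers washout.

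Several stronger readings are tempting, but the protocol does not support them.

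- A reader might infer from the bracket in 9.5 that serious thromboembolism or fracture escapes SAE reporting. It does not. The bracket removes listed events from the 9.5 time limit only; 9.2 and 9.3 bring the serious ones into SAE reporting.
- A reader might infer that women who never start have no safety follow-up. They are asked about listed events at every visit, and routine data cover the major diagnoses and death.
- A reader might treat an SAE during washout as caused by the trial. That would have to be judged case by case.
- A reader might try to size the gap from the background bone density figures or the 6-month adherence category. Bone density drift is not an SAE. The adherence category (Amber, 80-99%) includes women who started and then stopped or switched, so it is not a never-start rate.

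**Conclusion.** The point holds in a limited form. Section 9.5 leaves two things outside the reporting window: SAEs in consented women during a washout that the trial requires, and SAEs off the 9.2 list in randomised women before or without a first dose. The second conflicts with 2.2.2 and 9.3, and it makes the by-allocation summary of unlisted SAEs in 13.3 conditional on starting treatment. For randomised women, listed events are unaffected.

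The gap cannot be quantified from the protocol, and it may be small. The conclusion rests on two assumptions: that sites would follow the explicit dates in 9.5 rather than the undated duty in 9.3, and that no trial procedure outside the protocol covers washout. It is a cheap improvement to safety capture. It does not call the efficacy analysis into question.

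**What to change.** 1. Reword 9.5 to say that it governs SAEs, and state that 9.2 events meeting the SAE definition fall under the same reporting duty.
2. Set one rule for the start that covers every randomised woman from randomisation, whether or not she starts treatment, and consented women during washout. Report washout events separately, since they precede allocation.
3. Align the definition in 9.1, the duty in 9.3 and the summary in 13.3 with that rule, so that unlisted SAEs by allocated group include all randomised women.
4. Separately, reconcile 6.1, 8.2.1 and 8.3 on when the baseline DEXA is obtained relative to washout. The choice of rule is for the trial team.

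The cost is a protocol wording change and a date field on the SAE form. The downside is a few more SAE reports, including some for women who are never randomised.
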